#### 3.2. SCHEDULE OF EVENTS

Schedule of events can be found in appendix 1 of the protocol. The End of Study (EOS) visit must occur within 28 days of treatment discontinuation/completion and prior to initiation of any new anti-cancer therapy/regimen.

#### 3.3. Changes to Analysis from Protocol

No immunogenicity analyses are planned for the Exploratory/Biomarker objectives while the protocol mentioned.

For the efficacy endpoint overall survival, it was decided to present 6-month OS rate with median OS time.

#### 4. PLANNED ANALYSES

One interim analysis and one final analysis will be performed for this study.

Document: \\ieedc-vnac01\Biosdata\Genexine\GX-188E\GYA02599\Biostatistics\Documentation\SAP

Author: [name] Version Number: 1.1

Version Date: 05Sep2022

Template No: CS\_TP\_BS016 Revision 6 Reference: CS\_WI\_BS005

Effective Date: 02Dec2019

Analysis Plan Page 14 of 48

## 4.1. SAFETY MONITORING COMMITTEE (SMC)

The Safety Monitoring Committee (SMC) will be responsible for evaluating patients' safety data and determining the overall safety and tolerability profile of the investigational treatment regimen. The SMC will be comprised of the Sponsor Medical Monitor, and the Principal Investigator from each participating site.

Analysis for SMC review is not in IQVIA Biostatistics work scope and the relevant analysis methods for SMC review are not included in this SAP.

#### 4.2. INTERIM ANALYSIS

An interim analysis will be performed with safety and efficacy data in case of at least 22 patients in efficacy evaluation population, after obtaining week 10 tumor assessment results (by investigator/BICR).

## 4.3. FINAL ANALYSIS

The final analysis will be performed to report a primary CSR based on a data cut off after all 60 patients in the planned efficacy evaluation population have completed tumor assessment within 24 weeks by the investigator per RECIST v1.1

Since patient will be treated until they met one of the discontinuation criteria, some patients may still be ongoing at the time of final analysis. Therefore, a long-term follow-up study can be performed after final analysis with all available data (no cut-off date applied).

#### 5. Analysis Populations

Agreement and authorization of patients included/ excluded from each analysis population will be conducted prior to Database Lock.

#### 5.1. ALL PATIENTS SCREENED POPULATION

The all patients screened population will contain all patients who provide informed consent for this study.

Document: \\ieedc-vnac01\Biosdata\Genexine\GX-188E\GYA02599\Biostatistics\Documentation\SAP

Author: [name] Version Number: 1.1

Version Date: 05Sep2022

Template No: CS\_TP\_BS016 Revision 6 Reference: CS\_WI\_BS005

Effective Date: 02Dec2019

PROTOCOL GX-188E-005

Analysis Plan Page 15 of 48

#### 5.2. SAFETY POPULATION

The patients who receive at least 1 dose of 1 agent in the investigational treatment regimen (i.e. either GX-188E or P) will be included in the analysis of safety, regardless of the duration of treatment.

#### 5.3. DLT EVALUABLE POPULATION

Part A patients who receive all of the planned administrations of both agents (GX-188E and P) within the DLT-evaluation period (the first three weeks of treatment prior to Week 4 Day 1 visit), unless doses are missed within the first two weeks of treatment (i.e., Week 1 Day 1 to Week 2 Day 7) due to DLT(s).

#### 5.4. EFFICACY EVALUABLE POPULATION

All patients who complete the study will be included into the efficacy evaluable population. These patients will be identified by using the "Subject's status?" with answer "Completed trial" from end of study page of CRF.

All patients who discontinue the study treatment regimen early due to treatment-related toxicity will be considered evaluable for efficacy. These patients will be identified as those with DLT. Patients who discontinue study due to disease-related death, unequivocal tumor progression or with at least 1 post-baseline tumor assessment must have received at least 45 days on protocol treatment to be considered evaluable for efficacy. Patients who discontinue study due to disease-related death will be identified by using the "Primary reason for premature discontinuation from study" with answer "Death" from end of study page of CRF and the "Was death disease related" with answer "Yes" from death details page of CRF. Patients who discontinue study due to unequivocal tumor progression will be identified by using "Primary reason for premature discontinuation from study" with answer "Disease Relapse or Progression" from end of study page of CRF. Patients who discontinue study with at least 1 post-baseline tumor assessment will be identified as those with at least one RECIST/iRECIST Overall Response data on RECIST/iRECIST Overall Response page of CRF after screening visit. Patients in Part B and Part C who do not meet the aforementioned requirements will be considered non-evaluable for response and may be replaced. Patients from Part A, who receive the recommended Phase 2 regimen and who meet the aforementioned criteria for the Efficacy Evaluable Population will be included in the analysis for Part B and Part C. The following table provides further, more specific details.

Document: \\ieedc-vnac01\Biosdata\Genexine\GX-188E\GYA02599\Biostatistics\Documentation\SAP

Author: [name] Version Number: 1.1

Version Date: 05Sep2022

Template No: CS\_TP\_BS016 Revision 6 Reference: CS\_WI\_BS005

Analysis Plan Page 16 of 48

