# Dose modification and toxicity management of infusion-reactions related to pembrolizumab

Pembrolizumab may cause severe or life threatening infusion-reactions including severe hypersensitivity or anaphylaxis. Signs and symptoms usually develop during or shortly after drug infusion and generally resolve completely within 24 hours of completion of infusion. Dose modification and toxicity management guidelines on pembrolizumab associated infusion reaction are provided in Table 5.

Table 5. Pembrolizumab Infusion Reaction Dose modification and Treatment Guidelines

NCI CTCAE Grade	Treatment	Premedication at Subsequent Dosing
Grade 1 Mild reaction; infusion interruption not indicated; intervention not indicated	Increase monitoring of vital signs as medically indicated until the participant is deemed medically stable in the opinion of the investigator.	None
Grade 2 Requires therapy or infusion interruption but responds promptly to symptomatic treatment (e.g., antihistamines, NSAIDs, narcotics, IV fluids); prophylactic medications indicated for ≤24 hrs.	
 
Stop Infusion.
 
Additional appropriate medical therapy may include but is not limited to:
 
IV fluids
 
Antihistamines
 
NSAIDs
 
Acetaminophen
 
Narcotics
 
Increase monitoring of vital signs as medically indicated until the participant is deemed medically stable in the opinion of the investigator.
 
If symptoms resolve within 1 hour of stopping drug infusion, the infusion may be restarted at 50% of the original infusion rate (e.g. from 100 mL/hr. to 50 mL/hr.). Otherwise dosing will be held until symptoms resolve and the participant should be premedicated for the next scheduled dose.
 
Participants who develop Grade 2 toxicity despite adequate premedication should be permanently discontinued from further study drug treatment
 
	Participant may be premedicated 1.5h (± 30 minutes) prior to infusion of study interventionwith:  Diphenhydramine 50 mg po (or equivalent dose of antihistamine).  Acetaminophen 500-1000 mg po (or equivalent dose of analgesic).

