#### 24.4 Analysis Populations

Safety Population. All patients who receive at least 1 dose of 1 agent in the investigational treatment regimen (i.e. either GX-188E or P) will be included in the analysis of safety, regardless of the duration of treatment.

DLT-evaluable. Unless doses are missed within the first two weeks of treatment (i.e., Week 1 Day -1 to Week 2 Day 7) due to DLT(s), a patient must receive all of the planned administrations of both agents (GX-188E and P) within the DLT-evaluation period to be considered evaluable for DLT. If a patient misses any treatment within the first two weeks of the study for reasons other than a DLT, the patient will be considered non-evaluable for DLT and replaced.

Efficacy Evaluable Population. All patients who discontinue the study treatment regimen early due to treatment-related toxicity will be considered evaluable for efficacy. Patients who discontinue study due to disease-related death, unequivocal tumor progression or with at least 1 post-baseline tumor assessment must have received at least 45 days of treatment to be considered evaluable for efficacy. Patients in Part B and C who do not meet the aforementioned requirements will be considered non-evaluable for response and may be replaced. Patients from Part A, who receive the recommended Phase 2 regimen and who meet the aforementioned criteria for the Efficacy Evaluable Population will be included in the analysis for Part B and C. The following table provides further, more specific details.

Table 7. Determination of Patients to be Included in Efficacy Evaluable.

Patient Cohort	Reason for Discontinuation	Number of Days on Protocol Treatment	Include in Efficacy Evaluable Population (Yes/No)?
Part A receiving RP2 regimen*	Protocol-Defined Dose Limiting Toxicity (DLT), or other toxicity	Not applicable	Yes, included in Efficacy Evaluable Population
Part A receiving RP2 regimen*	Disease-related death, unequivocal tumor progression or at least 1 post-baseline tumor assessment	< 45 days	No
Part A receiving RP2 regimen*	Disease-related death, unequivocal tumor progression or at least 1 post-baseline tumor assessment	≥ 45 days	Yes, included in Efficacy Evaluable Population
Part A, receiving dose > RP2 regimen*	Any	Not applicable	No
Part B and C	Disease-related death, unequivocal tumor progression, or at least 1 post-baseline tumor assessment	< 45 days	No, patient may be replaced

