Part B and C	Disease-related death, unequivocal tumor progression, or at least 1 post-baseline tumor assessment	≥ 45 days	Yes, included in Efficacy Evaluable Population
Part B and C	Toxicity	Not applicable	Yes, included in Efficacy Evaluable Population

\*RP2 regimen = Recommended Phase 2 regimen of GX-188E

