#### Table 1. Determination of Patients to be Included in Efficacy Evaluable Population

Patient Cohort	Reason for Discontinuation	Number of Days on Protocol Treatment	Include in Efficacy Evaluable Population (Yes/No)?
Part A receiving RP2 regimen*	Protocol-Defined DLT, or other toxicity^	Not applicable	Yes, included in Efficacy Evaluable Population
Part A receiving RP2 regimen*	Disease-related death, unequivocal tumor progression or at least 1 post- baseline tumor assessment	< 45 days	No
Part A receiving RP2 regimen*	Disease-related death, unequivocal tumor progression or at least 1 post- baseline tumor assessment	≥ 45 days	Yes, included in Efficacy Evaluable Population
Part A, receiving dose > RP2 regimen*	Any	Not applicable	No
Part B and Part C	Disease-related death, unequivocal tumor progression, or at least 1 post-baseline tumor assessment	< 45 days	No, patient may be replaced
Part B and Part C	Disease-related death, unequivocal tumor progression, or at least 1 post-baseline tumor assessment	≥ 45 days	Yes, included in Efficacy Evaluable Population
Part B and Part C	Toxicity ^	Not applicable	Yes, included in Efficacy Evaluable Population

\*RP2 regimen = Recommended Phase 2 regimen of GX-188E

 $Document: \underline{\label{locality} Nocumentation} Biosdata \underline{\label{locality} GX-188E\underline{\label{locality} GYA02599\underline{\label{locality} Biosdata}} \\$ 

Author: [name] Version Number: 1.1

Version Date: 05Sep2022

Template No: CS\_TP\_BS016 Revision 6 Reference: CS\_WI\_BS005

Effective Date: 02Dec2019

^ Toxicity = Any dose limiting toxicity (DLT).

Analysis Plan Page 17 of 48

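### The SAP narrows the protocol's treatment-related toxicity rule to DLTs, so some early toxicity stops in Parts B and C can leave the primary ORR24 denominator, and SAP 3.3 does not list the change

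*SAP*

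**What the plan says.** Protocol 24.4 states: "All patients who discontinue the study treatment regimen early due to treatment-related toxicity will be considered evaluable for efficacy". In Protocol Table 7 the Part B and C toxicity row gives days on treatment as not applicable and the result "Yes, included in Efficacy Evaluable Population". The Part A row of that table names DLT and other toxicity separately, so the protocol did not treat the two as the same.

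SAP 5.4 repeats the protocol sentence and then adds "These patients will be identified as those with DLT". The footnote to SAP Table 1 reads "Toxicity = Any dose limiting toxicity (DLT", and it is attached to a Part A row that reads "Protocol-Defined DLT, or other toxicity". The SAP table therefore disagrees with itself as well as with the protocol.

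For a patient who discontinues, the other routes into the population (disease-related death, progression, or at least one post-baseline assessment) require at least 45 days on treatment. Below that, the Part B and C entry is "No, patient may be replaced".

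SAP 3.3 lists two departures from the protocol. One is that the immunogenicity analyses are not planned. The other is "For the efficacy endpoint overall survival, it was decided to present 6-month OS rate with median OS time". The toxicity definition is not mentioned.

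**The concern.** ORR24 is defined on efficacy evaluable patients (SAP 15.1), and SAP 8 runs the efficacy analysis on that population. The rule for toxicity stops therefore sets the primary denominator. A DLT is a much narrower thing than a treatment-related toxicity that ends treatment: it has a window of the first three weeks, listed criteria with exemptions, and a CRF flag. A program written from the SAP would build a different primary population from the protocol's.

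The trial is single-arm and compares ORR24 with a fixed 12.2%. Dropping patients who are mostly non-responders pushes the estimate towards success, and nothing in SAP 3.3 would alert a reader to it.

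**Working it through.** **Who can fall through.**
- The DLT window is the first 3 weeks, or 21 days (SAP 16.1.7). A related toxicity that begins between about day 22 and day 44 and ends treatment in that period is outside the listed DLT criteria and short of 45 days.
- Some Cycle 1 stops are also affected. For infusion reactions, Protocol Table 5 says: "Participants who develop Grade 2 toxicity despite adequate premedication should be permanently discontinued from further study drug treatment". Non-hematologic DLT criteria start at Grade 3, so this Grade 2 stop does not meet them. Hypersensitivity reactions lasting 72 hours or less are exempt at any grade.
- A patient who stops for non-DLT toxicity at 45 days or later with no post-baseline assessment also meets no route. The first scheduled scan is at about 9 weeks (63 days), although Protocol 22.1.3 asks for imaging at discontinuation.
- Two exceptions keep a patient in: a CRF status of trial completed (SAP 5.4), or an event called a DLT under the discretionary clause.

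**Direction.** With the first scan at about 9 weeks (Protocol 22.1.2), most patients who stop before 45 days would have no response recorded. Imaging should continue after a stop without progression (Protocol 22.1.3), so a later response is possible.

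**The plan's own figure first.** Inputs from Protocol 24.3: null 12.2%, alternative 37%, two-sided 5%, 97% power, 25% dropout, N = 60. Success means that the lower limit of the two-sided 95% Clopper-Pearson interval exceeds 12.2%.
- At n = 45: 10/45 has lower limit 11.20% (fails) and 11/45 has 12.88% (passes), so 11 responders are needed. P(X ≥ 11 | 45, 0.37) = 97.4%.
- 45/(1 - 0.25) = 60. The stated sample size reproduces.
- At n = 60: 13/60 has lower limit 12.07% (fails) and 14/60 has 13.38% (passes), so 14 are needed.

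**Effect of dropping a share d, with replacement.** The documents give no value for d, so it is an assumption. Taking all dropped patients as non-responders gives an upper bound. The rate among evaluable patients is then p/(1-d), which is p times 1.02, 1.05 or 1.11 at d = 2%, 5% or 10%. False success in Part C is P(X ≥ r | n, 0.122/(1-d)):

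| d | evaluable rate | n = 60, r = 14 | n = 45, r = 11 |
|---|---|---|---|
| 0 | 12.20% | 1.2% | 1.7% |
| 2% | 12.45% | 1.4% | 2.0% |
| 5% | 12.84% | 1.8% | 2.4% |
| 10% | 13.56% | 2.8% | 3.5% |

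The 2.5% upper tail is reached at about d = 8.8% (n = 60) or 5.3% (n = 45). The n = 60 column is itself a bounding case: Protocol 10.5 caps recruitment at 60, so replacing up to 60 evaluable patients would exceed the cap.

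**Without replacement.** From 60 treated, dropping one to six non-responders lowers the responders needed from 14 to 13: 13/59 has lower limit 12.29% and passes, where 13/60 fails. From 45, it takes four: 10/41 has lower limit 12.36% and passes, where 10/45 fails.

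**Power.** At a true 37%, success is already 99% (n = 60) or 97% (n = 45). What suffers is the estimate and the error rate, not power.

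**The case against.** Several features narrow the gap.
- The discretionary clause lets the investigator and the medical monitor call other treatment-limiting events a DLT, and a toxicity that ends treatment fits that description well. Nothing limits the CRF flag to Part A; only the DLT summary tables are so limited. But the clause is permissive and the stated window is three weeks, so it cannot guarantee what the protocol makes automatic.
- SAP 5 requires agreement on population membership before database lock. That is a review point, but it does not change the written rule.
- Protocol 19.1 says that stopping treatment is not withdrawal from the study, so some of these patients may later be recorded as having completed the trial. How often depends on a CRF that is not in the documents.
- SAP 15 repeats ORR24 in the safety population, which keeps every treated patient and would show a distortion. It is labelled a sensitivity analysis, and the success criterion does not rest on it.
- The numbers are modest. Part of the one-patient reversal is the step in the exact limit: a clean rule of 13 out of 59 has 2.4% false success with nobody excluded.

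A reader might also infer that every Grade 3 or 4 infusion reaction that ends treatment drops out. The documents do not support that. The 72-hour exemption covers reactions classed as hypersensitivity; another treatment-related Grade 3 or 4 reaction in Cycle 1 that meets no other exemption is a DLT and stays in.

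**Conclusion.** The conflict is real and should be corrected before the analysis. Following the SAP as written gives a primary denominator that is not the protocol's, the change is not disclosed, and the likely bias is upward. This rests on the wording and needs no assumption about d.

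The size does need one. If all dropped patients are non-responders and are replaced, Part C false success rises from 1.2% to between 1.8% and 2.8% at n = 60, or from 1.7% to between 2.4% and 3.5% at n = 45, for d of 5% to 10%. A reader might infer that the Part C error rate is broken. The documents do not show that: they give no rate of such stops, and with replacement the error stays under 2.5% when d is small. What can be said without a rate is that one excluded non-responder is enough to turn a fail into a pass at the margin.

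**What to change.** Change the SAP only.
- In SAP 5.4, delete the sentence that identifies these patients as those with a DLT. Delete the Table 1 footnote that equates toxicity with DLT.
- Identify them by toxicity as the recorded reason for stopping the study treatment regimen, supported by a treatment-related AE with the action recorded as drug withdrawn.
- Define how a stop of only one agent is classified. Otherwise a patient taken off one agent who then progresses before 45 days could be counted as a toxicity stop, against the progression row of Protocol Table 7.
- Keep these patients in the ORR24 denominator as non-responders unless a response within 24 weeks is confirmed.

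A separate issue is whether the rule that removes patients with unconfirmed responses could exclude the same patients. It stands in both documents (Protocol synopsis and 22.2; SAP 3.1 and 15.1) and has to be reconciled in both, so it is not part of this change.

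The cost is SAP wording and one programming rule. The fields are already in use: reason for medication withdrawal (SAP 9), relatedness (16.1.2) and action taken (16.1.3). No planned sample size changes. The reported ORR24 may be slightly lower.

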#### Table 1. Determination of Patients to be Included in Efficacy Evaluable Population

Patient Cohort	Reason for Discontinuation	Number of Days on Protocol Treatment	Include in Efficacy Evaluable Population (Yes/No)?
Part A receiving RP2 regimen*	Protocol-Defined DLT, or other toxicity^	Not applicable	Yes, included in Efficacy Evaluable Population
Part A receiving RP2 regimen*	Disease-related death, unequivocal tumor progression or at least 1 post- baseline tumor assessment	< 45 days	No
Part A receiving RP2 regimen*	Disease-related death, unequivocal tumor progression or at least 1 post- baseline tumor assessment	≥ 45 days	Yes, included in Efficacy Evaluable Population
Part A, receiving dose > RP2 regimen*	Any	Not applicable	No
Part B and Part C	Disease-related death, unequivocal tumor progression, or at least 1 post-baseline tumor assessment	< 45 days	No, patient may be replaced
Part B and Part C	Disease-related death, unequivocal tumor progression, or at least 1 post-baseline tumor assessment	≥ 45 days	Yes, included in Efficacy Evaluable Population
Part B and Part C	Toxicity ^	Not applicable	Yes, included in Efficacy Evaluable Population

\*RP2 regimen = Recommended Phase 2 regimen of GX-188E

 $Document: \underline{\label{locality} Nocumentation} Biosdata \underline{\label{locality} GX-188E\underline{\label{locality} GYA02599\underline{\label{locality} Biosdata}} \\$ 

Author: [name] Version Number: 1.1

Version Date: 05Sep2022

Template No: CS\_TP\_BS016 Revision 6 Reference: CS\_WI\_BS005

Effective Date: 02Dec2019

^ Toxicity = Any dose limiting toxicity (DLT).

Analysis Plan Page 17 of 48

### 6. GENERAL CONSIDERATIONS

#### 6.1. REFERENCE START DATE AND STUDY DAY

Study Day will be calculated from the reference start date and will be used to show start/ stop day of assessments and events.

Reference start date is defined as the day of the first dose of study medication (either GX-188E or P, whichever occurred first), Day 1 is the day of the first dose of study medication and will appear in every listing where an assessment date or event date appears.

- If the date of the event is on or after the reference date, then:
  - Study Day = (date of event reference date) + 1.
- If the date of the event is prior to the reference date, then:
  - Study Day = (date of event reference date).

In the situation where the event date is partial or missing, study day, and any corresponding durations will appear partial or missing in the listings.

#### 6.2. BASELINE

Unless otherwise specified, baseline is defined as the last non-missing measurement (including unscheduled assessments) taken prior to reference start date and time. Reference start date and time is defined as the date and time of the first dose of study medication (either GX-188E or P, whichever occurred first). In the case where the time is unknow and last non-missing measurement and the reference start date coincide, that measurement will be considered prebaseline, but AEs and medications commencing on the reference start date will be considered post-baseline.

## 6.3. RETESTS, UNSCHEDULED VISITS AND EARLY TERMINATION DATA

In general, for by-visit summaries, data recorded at the nominal visit will be presented. Unscheduled measurements will not be included in by-visit summaries but will contribute to the best/worst case value where required (e.g. shift table).

 $Document: \underline{\label{locality} Nieedc-vnac01\\Biosdata\\Genexine\\GX-188E\\GYA02599\\Biostatistics\\Documentation\\SAP}$ 

Author: [name] Version Number: 1.1

Version Date: 05Sep2022

Template No: CS\_TP\_BS016 Revision 6 Reference: CS\_WI\_BS005

PROTOCOL GX-188E-005

Analysis Plan Page 18 of 48

In the case of a retest (same visit number assigned), the latest available measurement for that visit will be used for by-visit summaries.

Listings will include scheduled, unscheduled, retest and early discontinuation data.

